For both groups, the Scrambler machine was kept behind a curtain to help preserve masking. The machine itself was turned on for all participants, though without emitting any stimulation in those receiving sham, so that the alert indicating termination of treatment would be heard by all participants regardless of treatment assignment. Because treatment effect has been shown to vary across technicians, one technician was trained in the proper delivery of Scrambler treatment and performed all interventions.

Study objectives and measures:

Our primary objective was to test the hypothesis that Scrambler therapy is an effective, acceptable, feasible and safe treatment of persistent central neuropathic pain for patients with NMOSD. To test this hypothesis, we performed a randomized single blind, sham-controlled trial testing Scrambler therapy in patients with NMOSD. The primary outcome was feasibility and acceptability. Secondary endpoints included both safety and effectiveness at the end of the 10-day treatment period. Feasibility of treatment was examined to determine whether the intervention was appropriate for this patient population, toward the effort of informing a larger, Phase III study. This was measured by assessing the following: 1) adherence to visit schedule and 2) response to the following question asked directly after completion of the 10-day treatment period: "Do you think you received treatment?" (Yes/No). Acceptability was measured by assessing response to the following question, also asked directly following the treatment course: "Would you want to continue treatment in clinic, if available?" (Yes/No).

Safety of the intervention was evaluated by comparing Adverse Events (AEs) and Serious Adverse Events (SAEs) in the treated versus sham groups. These were monitored and documented prior to initiation of each treatment daily, at termination of final treatment, and at 30- and 60-day follow-up.

Effectiveness was evaluated based on degree of improvement in pain, comparing the treatment group to sham. Prior to initiation of Scrambler therapy and at completion of treatment, patients were asked to rate their pain by the 11-point NRS score. Patients additionally reported NRS pain

scores at 30- and 60- days following therapy completion to assess sustainability of treatment effect.

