Although not powered appropriately, an exploratory objective aimed to assess the relationship between improved pain and other co-occurring symptoms. Prior to initiation of Scrambler therapy, patients were asked to complete each of the following measurement tools to determine baseline pain severity and interference, anxiety, depression, and sleep disturbance, respectively: Brief Pain Inventory (BPI), Neuro-QoL [Quality of Life in Neurological Disorders] Short Form v1.0 - Anxiety, Neuro-QoL Short Form v1.0 - Depression, and Neuro-QoL Short Form v1.0 - Sleep Disturbance. Measurement tools were accessed by participants via a secure online portal. Participants were provided with an alphanumeric code that enabled their responses to be linked to their demographic and clinical data in a confidential manner. Questionnaires were mailed to participants without internet access with a postage-paid envelope provided for return of questionnaires. Patients again completed all measurement tools at end of treatment, and at 30- and 60-days following end of treatment.

Statistical analysis:

As one measure of feasibility of treatment, adherence to visit schedule was ascertained. We report the number of patients in each group who were able to complete all treatments. Fisher's exact test was performed to assess if adherence is independent of group assignment. For each of the two survey questions used to assess feasibility and acceptability, as described above, a 95% confidence interval for the proportion of participants answering "Yes" was calculated.

Given the small number of patients in the study, exact binomial confidence intervals were calculated since normal distribution could not be assumed.

Descriptive statistics were used to report AEs and SAEs. Incidence and severity were compared between groups.

Effectiveness was based on degree of improvement of pain and compared NRS pain scores in the treatment group and sham group using the Friedman One-Way Repeated Measure Analysis of Variance by Ranks test at baseline, following treatment, and at 30- and 60-day follow-up.

Wilcoxon signed-rank testing was used to determine sustainability over time by comparing scores at baseline to those following treatment, at 30-day follow-up and at 60-day follow-up. A chi-squared analysis comparing the number of treated patients who thought they received treatment versus the number of sham patients who thought they received treatment was performed to determine if masking was effective.

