The target sample size of 22 (11 per arm) was based on previous studies which suggest that the average pain value at baseline is at least 4 on the 0-10 NRS with a standard deviation of the original pain value expected to fall in the range of 1-1.5 in this patient population. A conservative estimate of the standard deviation of the change across patients from Day 1 to Day 10 was approximately up to 2. With 11 patients in each arm and under these assumptions, we were able to detect a change of 2.5 points in the Scrambler group at 80% power, with a difference in proportions of 60% between the two groups.

To explore the impact on co-occurring symptoms when intervening on pain, scores were tabulated for each of the following based on measurement tool data: anxiety, depression, sleep

disturbance and pain interference. Friedman One-Way Repeated Measure Analysis of Variance by Ranks was tabulated for each symptom, comparing the change at baseline, following treatment, and at 30- and 60-day follow-up timepoints in each arm. A subanalysis was similarly conducted in those patients who “responded” to Scrambler treatment versus sham. Based on a cohort of adult patients with spinal cord injury who reported clinically meaningful change in pain over time, “response” was defined as patients with a decrease in NRS pain scores of 1.80 points between baseline and end of treatment.

Demographic and clinical characteristics were compared between Scrambler and sham groups using Mann-Whitney *U* and Chi-squared testing, as appropriate.

Data availability:

Public Law 110-85 (also known as the FDA Amendments Act of 2007) mandates registration and results reporting of "applicable clinical trials" in ClinicalTrials.gov. We support efforts to promote data sharing toward the advancement of science and registered this clinical trial, providing trial design, eligibility criteria and outcomes measures.

Classification of evidence:

This study provides Class II evidence of Scrambler therapy use in patients diagnosed with NMOSD who have central neuropathic pain.

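### The Scrambler-versus-sham comparison of pain is assigned to a Friedman test, which contains no arm term, so no named analysis tests whether Scrambler beats sham

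*Combined protocol and SAP*

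**What the plan says.** Under Study objectives and measures, the question is between arms: "Effectiveness was evaluated based on degree of improvement in pain, comparing the treatment group to sham". The time point is also fixed there: "Secondary endpoints included both safety and effectiveness at the end of the 10-day treatment period".

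Under Statistical analysis, the effectiveness paragraph says the plan "compared NRS pain scores in the treatment group and sham group using the Friedman One-Way Repeated Measure Analysis of Variance by Ranks test", with four repeated measurements: "at baseline, following treatment, and at 30- and 60-day follow-up". The only other named test of the NRS is for durability: "Wilcoxon signed-rank testing was used to determine sustainability over time by comparing scores at baseline to those following treatment", and likewise for the two follow-up visits.

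For anxiety, depression, sleep and pain interference, Friedman is used by "comparing the change at baseline, following treatment, and at 30- and 60-day follow-up timepoints in each arm". A responder analysis follows: "A subanalysis was similarly conducted in those patients who “responded” to Scrambler treatment versus sham". Response is a fall of 1.80 NRS points by end of treatment, but no test of response rates between arms is named.

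Between-arm tests do appear, for other quantities. On adherence: "Fisher's exact test was performed to assess if adherence is independent of group assignment". A chi-squared test addresses masking, and Mann-Whitney and chi-squared tests address demographic and clinical characteristics. Adverse events are compared descriptively.

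**The concern.** The question is whether Scrambler reduces pain more than sham. The named method answers a different one: whether scores change over time.

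Scores can fall in both arms for reasons unrelated to the device. Sham response and natural fluctuation are two. Regression to the mean is a third, since entry requires an NRS of at least 4. A sham arm exists to subtract these, and that happens only if the arms are compared directly. A significant p-value in one arm and a non-significant one in the other is not a test of the difference and does not hold the type I error.

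There are two further mismatches. The endpoint is end of treatment, but the Friedman statistic also mixes in Day 30 and Day 60. And the standard test needs all four scores, so a patient missing any one visit is lost even if the end-of-treatment score is present.

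**Working it through.** **What the statistic contains.** With k = 4 visits, n patients, and R_j the sum over patients of the within-patient rank at visit j:

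Q = 12/[n·k(k+1)] · ΣR_j² − 3n(k+1) = (0.6/n)·ΣR_j² − 15n, referred to chi-squared on 3 df.

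No term identifies the arm. There are three possible readings of the plan:

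- *Per arm* (n = 11 twice), as for the other symptoms: two within-arm p-values and no comparison.
- *Pooled* (n = 22): a test of a time effect averaged over arms.
- *Arm as the repeated factor*: this needs patients matched across arms. Randomization and Masking describes stratified blocks, not pairs.

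**Which test the sample size fits.** Inputs from the sample-size paragraph: 11 per arm, 2.5-point change, SD of change 2, 80% power. Two-sided alpha of 0.05 is assumed because none is stated.

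- Two-sample t: noncentrality 2.5/[2·√(2/11)] = 2.93 on 20 df, power **79.6%**.
- Within-arm paired t: noncentrality 2.5/[2/√11] = 4.15 on 10 df, power 96.1%.

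The stated 80% is reproduced by a between-arm test of change, which the analysis paragraphs never name. Mann-Whitney on the same change has about 77% power (20,000 simulated trials, normal data).

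**Error rates with no Scrambler effect.** From the documents: 11 per arm, SD of change 2, and a baseline SD of 1.25 (middle of the stated 1 to 1.5). Assumed: baseline mean 6, correlation 0.5 between post-baseline changes, the same improvement in both arms lasting to Day 60, normal scores, threshold 0.05. There were 5,000 trials per row.

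| Improvement in both arms | Friedman significant in Scrambler only | Friedman on all 22 significant | Mann-Whitney on end-of-treatment change |
|---|---|---|---|
| 0 | 4.2% | 4.4% | 4.6% |
| 1.0 | 18.2% | 50.1% | 4.4% |
| 1.5 | 25.4% | 87.3% | 4.9% |
| 2.0 | 16.5% | 98.8% | 4.4% |
| 2.5 | 6.0% | 99.9% | 5.0% |

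The Scrambler-only column is one-directional, so its fair comparator is 2.5%, half of a two-sided 5%.

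Repeating this with integer scores limited to 0–10 and correlations of 0.3 to 0.7 gives Scrambler-only rates of 18–20%, 25–27% and 12–15% at 1, 1.5 and 2 points. At 0.5 points the rate is about 8–9%, and at 3 points it is under 1%. In a similar integer-score run with baseline SD 1.5, ANCOVA rejected in 5.1–5.3% of null trials.

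The pooled test can also point the wrong way. With a true 2.5-point benefit and no sham improvement it is significant in 51.5% of trials, fewer than the 98.8% when both arms improve by 2 points and Scrambler adds nothing.

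**Loss from requiring four scores.** Let m be the assumed fraction missing at each of three post-baseline visits. If visits are missed independently, 11·(1−m)³ remain per arm: 9.4 at m = 5% and 6.8 at m = 15%. If the same patients miss every visit, 11·(1−m) remain: 10.5 and 9.4.

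**The case against.** The strongest reply has four parts.

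*A between-arm comparison was clearly intended.* The objectives say so, and the sample-size paragraph mentions a 60-point difference in proportions between groups, which suggests a responder comparison. The intent is not in dispute. But neither the event nor the test behind that difference is named, and the responder definition is used only to subset the symptom analysis.

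*The decision rule is imputed.* The plan does not say that significance in Scrambler but not in sham would count as success, nor whether Friedman is run per arm or pooled for pain. A pooled Friedman that detects a time effect is correct for its own null. This stands. The simulated rates show what follows if the output is read as a treatment effect, which is the use the plan assigns to it.

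*The size depends on chosen inputs.* This also stands. The documents give no baseline mean beyond at least 4, no sham improvement, no correlation between visits and no attrition rate. The inflation peaks near 1.5 points and vanishes at 0 and at 3 or more. The lower missing-data figures need independent missingness, and dropping incomplete patients is the default of the standard test, not a documented rule.

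*Effectiveness is secondary.* Feasibility and acceptability are primary. However, the primary hypothesis includes effectiveness, the title claims improved pain, the sample size rests on pain change, and the study is meant to inform a Phase III trial.

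None of these supplies the missing test.

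**Conclusion.** The concern holds. The mismatch follows from the form of the test and needs no simulation: a one-way Friedman test cannot compare Scrambler with sham, and no other named analysis of the NRS does so. The claim is confined to pain effectiveness, since adherence, masking and patient characteristics do have between-arm tests.

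Its practical size depends on how far both arms improve together. For a shared improvement of 1 to 2 points, a false Scrambler-only finding is roughly 5 to 10 times as likely as the nominal 2.5%. With no shared improvement it is about 4%. These rates rest on the assumed baseline mean, correlation, persistence of improvement and alpha given above. The matter should be corrected before any effectiveness result is reported, because as written the plan cannot answer its own effectiveness question.

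**What to change.** Name one between-arm analysis of NRS at end of treatment: ANCOVA of the end-of-treatment score on arm with baseline NRS as covariate, or a Mann-Whitney or permutation test on the change. Include every randomized patient with an end-of-treatment score. State alpha, sidedness and how the stratification factors are handled. Baseline NRS largely carries the pain-level stratum; medication class could enter as a sensitivity analysis, given only 22 patients.

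Report the Scrambler-minus-sham difference with a 95% confidence interval. With SD 2 and 11 per arm, an unadjusted interval would be about ±2.086·2·√(2/11) = ±1.8 points, so the estimate matters more than the p-value.

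Keep Friedman and signed-rank results as within-arm description. For Day 30 and Day 60, the same between-arm difference can be estimated by visit. A mixed model with arm-by-visit terms is one option, but the main gap closes without it. If a responder comparison is intended, name the event and the test.

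The cost is a revised paragraph and a few lines of code, with no new patients or data. The document is written in the past tense, so if outcomes have already been seen, label the analysis as added afterwards. The between-arm result may look less favourable than the within-arm p-values.

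### Sustainability is tested only against baseline and without the sham arm, so the tests cannot tell a larger benefit partly lost from a smaller one fully kept, or a lasting treatment effect from change that sham would also show

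*Combined protocol and SAP*

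**What the plan says.** In the combined protocol and SAP, Study objectives and measures says that patients gave NRS "scores at 30- and 60- days following therapy completion to assess sustainability of treatment effect". The same section defines effectiveness as a comparison of the treated group with sham.

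Under Statistical analysis, the method for sustainability is: "Wilcoxon signed-rank testing was used to determine sustainability over time by comparing scores at baseline to those following treatment, at 30-day follow-up", and again at 60 days. Baseline is therefore the reference in all three contrasts. The section does not say in which arm or arms the signed-rank tests are run.

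The other analysis of these scores is the "Friedman One-Way Repeated Measure Analysis of Variance by Ranks test at baseline, following treatment, and at 30- and 60-day follow-up". The plan gives no contrast of end of treatment with day 30 or day 60, no retained fraction, and no definition of a sustained effect.

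**The concern.** Whether an effect is sustained has two parts: how much of the gain at end of treatment is still there later, and whether what remains is due to treatment.

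The planned tests address neither directly. The contrast of baseline with end of treatment measures the initial change and says nothing about persistence. The day-30 and day-60 contrasts depend, for a given SD, only on the level at that visit and not on the level from which it came.

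A signed-rank test within an arm also makes no use of the control. Patients had to have an NRS of 4 or more to enter (Participants), so some fall from baseline could occur under sham through regression to the mean or placebo response.

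At stake is the trial's statement on durability, which supports a secondary question.

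**Working it through.** **Inputs**
- Patients: "The target sample size of 22 (11 per arm) was based on previous studies" (Statistical analysis).
- SD of change: "A conservative estimate of the standard deviation of the change across patients from Day 1 to Day 10 was approximately up to 2" (same section). It is given only for Day 1 to Day 10. Using it at days 30 and 60 is an assumption, so 1.5 and 1 are shown as well.
- Planned effect: "we were able to detect a change of 2.5 points in the Scrambler group at 80% power" (same section).
- Assumed, because not stated: two-sided 5% level; correlation of 0.5 to 0.8 between the change at end of treatment and the change at follow-up.

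**1. The plan's own figure.** Two-sample t-test: SE = 2 × √(2/11) = 0.853, noncentrality = 2.5/0.853 = 2.93, df = 20. Power is 79.6%, which reproduces the stated 80%. Read as a one-sample test in the Scrambler arm, power would be 96.1%. The 2.5 points is thus a between-arm figure, and using it below as the fall from baseline in the Scrambler arm assumes no change under sham.

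**2. What the baseline contrast can tell.** Exact two-sided signed-rank test, n = 11, rejecting if the smaller rank sum is 10 or less (actual level 0.042). Normal changes, 60,000 simulated trials per case. Probability that follow-up is significantly different from baseline:

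| Mean benefit, end of treatment → follow-up | SD 2 | SD 1.5 | SD 1 |
|---|---|---|---|
| 2.5 → 1.25 (half lost) | 0.42 | 0.65 | 0.94 |
| 1.25 → 1.25 (kept) | 0.42 | 0.65 | 0.94 |
| 3 → 1.5 (half lost) | 0.56 | 0.81 | 0.99 |
| 1.5 → 1.5 (kept) | 0.56 | 0.81 | 0.99 |
| 4 → 2 (half lost) | 0.81 | 0.97 | 1.00 |
| 2 → 2 (kept) | 0.81 | 0.97 | 1.00 |

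Within each pair the follow-up test behaves identically, whatever the SD. This is the core of the point, and it needs no assumed rule for calling an effect sustained.

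**3. What a contrast with end of treatment can tell.** With SD 2 for each change, the SD of the within-patient change from end of treatment to follow-up is 2 × √(2(1 − ρ)): 2.00 at ρ = 0.5 and 1.27 at ρ = 0.8.
- A loss of 1.25 points is detected with probability 0.42 (ρ = 0.5) or 0.80 (ρ = 0.8). A fully kept benefit is flagged as a loss in about 2% of trials, whatever its size.
- 95% CI half-width = t(0.975; 10) × SD/√11 = 2.228 × 2.00/3.317 = 1.34 points, or 2.228 × 1.27/3.317 = 0.85 points.

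This contrast does separate the two cases. With 11 patients it is imprecise, so a non-significant result on it would not prove retention either.

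**4. Between-arm difference at follow-up.** 95% CI half-width = t(0.975; 20) × 2 × √(2/11) = 2.086 × 0.853 = 1.78 points at SD 2.

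**The case against.** **Comparison with baseline is legitimate.** It asks whether patients are still better than when they started, which matters to them. This stands: the tests should be kept.

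**The three contrasts together show the pattern.** A reader who sees results at all four times can see a rebound. This stands in part. At SD 2, the 2.5-point case is significant at end of treatment in 94% of trials and the 1.25-point case in 42%, so the set carries some information. But comparing one p-value with another is not a test of the change between the two visits, and gives no interval for it.

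**The Friedman test covers all four times.** It is an omnibus test. The initial drop alone can make it significant. It isolates neither the loss after treatment nor a between-arm difference at day 30 or 60, although the plan's sentence names both groups.

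**A stronger reading is tempting:** that the plan will call a half-lost benefit sustained and a kept one lost. The documents do not support it, for these reasons:
- They never say that significance against baseline means sustained, or that its absence means lost.
- At the plan's own 2.5 points and SD 2, a half-lost benefit is significant in only about 42% of trials. The 81% in the table needs a 4-point drop, which no document gives as an expected effect.
- A fully kept 1.5-point benefit misses significance in about 44% of trials at SD 2, but in 19% at SD 1.5 and 1% at SD 1. Among trials already significant at end of treatment, the SD 2 figure is 21% to 31%.

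A reader might also infer that a Phase III trial would take its follow-up length from this result. The text links Phase III to feasibility only.

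**Conclusion.** The point holds in limited form. The signed-rank tests answer whether pain is still below baseline. They do not measure how much of the end-of-treatment gain is kept, and they do not separate a lasting treatment effect from change that would also occur under sham.

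At n = 11, a benefit of 2.5 falling to 1.25 and one of 1.25 fully kept give the same chance of a significant follow-up test: about 42% at SD 2 and 65% at SD 1.5. That equality follows from the choice of reference. The percentages rest on a two-sided 5% level, normal changes, and an SD at follow-up borrowed from Day 1 to Day 10.

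This is a mismatch between question and test on a secondary matter. It does not show that the trial's durability conclusion is wrong.

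**What to change.** Keep the baseline contrasts, describe them as tests of remaining improvement, and name the arm or arms in which they are run. Then add:

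1. The within-patient change in NRS from end of treatment to day 30 and to day 60, with a 95% CI, interpreted only if a benefit over sham is seen at end of treatment. Without that condition, a treatment that never worked would show no rebound and look durable.
2. The Scrambler-minus-sham difference in change from baseline at days 30 and 60, with a 95% CI.

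Base the durability statement on these estimates. Do not read a non-significant result as benefit kept or as benefit lost.

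Do not use 1.80 points as a margin for the mean rebound. In the plan it defines response in a single patient from baseline to end of treatment. As a margin it would allow a loss of 1.80/2.5 = 72% of the planned effect. Requiring the upper bound of the rebound to lie below it would be met in about 77% of trials of a treatment with no effect (SD of rebound 2), or about 99% (SD 1.27).

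The cost is SAP wording and two sets of estimates from scores already collected. The document is written in the past tense, so if results have been seen, the additions should be labelled as such. The intervals will be wide with 11 per arm, and the durability statement will be more cautious.

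### Pain effectiveness is defined as improvement over sham at end of treatment, but the analysis section gives no between-group NRS test at that time point and no alpha or testing order

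*Combined protocol and SAP*

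**What the plan says.** Under Study objectives and measures, the plan fixes the role, the time point and the comparator for pain:

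- "The primary outcome was feasibility and acceptability", so pain is not primary.
- "Secondary endpoints included both safety and effectiveness at the end of the 10-day treatment period".
- "Effectiveness was evaluated based on degree of improvement in pain, comparing the treatment group to sham".
- The later visits have a different purpose. Patients report "scores at 30- and 60- days following therapy completion to assess sustainability of treatment effect".

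The Statistical analysis section then assigns effectiveness to the "Friedman One-Way Repeated Measure Analysis of Variance by Ranks test at baseline, following treatment, and at 30- and 60-day follow-up", and adds a second set of tests: "Wilcoxon signed-rank testing was used to determine sustainability over time by comparing scores at baseline to those following treatment, at 30-day follow-up and at 60-day".

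The sample-size paragraph works from the change between Day 1 and Day 10. The responder definition also uses baseline to end of treatment.

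No significance level is given for any test; the only related figure is the 95% confidence level for the two survey questions. No adjustment, testing order or gate is given for the pain tests.

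**The concern.** The endpoint and the tests do not match. The endpoint is a difference from sham at one visit. Each planned signed-rank test compares a visit with baseline. A one-way Friedman test in its usual form ranks the visits within each patient and has no term for group. The effectiveness sentence says the two groups are compared but not how group enters the test. If it is run by arm, as the plan describes for the co-occurring symptoms, it too is a within-arm test.

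A significant fall from baseline in the Scrambler arm may reflect expectation, regression to the mean after entry at NRS 4 or higher, or natural course. The sham arm is there to remove these effects, and a within-arm test does not use it.

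The tests can also disagree. Friedman may be non-significant while one visit is significant, or end of treatment may be non-significant while day 30 is significant. The plan does not say which result settles the question.

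This matters because the pain tests are not labelled exploratory; only the co-occurring symptoms are. The objective reads "Our primary objective was to test the hypothesis that Scrambler therapy is an effective, acceptable, feasible and safe treatment", and the document closes with "This study provides Class II evidence of Scrambler therapy use in patients diagnosed with NMOSD who have central neuropathic pain".

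**Working it through.** **1. The plan's own figure.** Inputs from the sample-size paragraph: 11 per arm, a change of 2.5 points, SD of change up to 2, power 80%. Alpha is not stated; two-sided 5% is assumed.

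- Standard error of a between-group difference: 2 × √(2/11) = 0.853.
- Noncentrality: 2.5 / 0.853 = 2.93 on 20 degrees of freedom.
- Two-sample t power: 79.6%, which reproduces the stated 80%.
- The same calculation at two-sided 2.5% or 10% gives 69.3% or 88.2%.
- A one-arm paired t-test with 11 patients gives 96.1%.

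The stated power therefore fits a Scrambler-versus-sham comparison of Day 1 to Day 10 change at two-sided 5%. It does not fit a within-arm test.

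**2. Endpoint against tests.**

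| | Objectives and sample size | Statistical analysis |
|---|---|---|
| Comparator | Sham | Own baseline (signed-rank); group role unclear (Friedman) |
| Time point | End of treatment | Four visits together, then three visits separately |
| 30 and 60 days | Sustainability | Tested alongside end of treatment |
| Level, order, gate | Not stated | Not stated |

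**3. No true change, Scrambler arm only.** Each test is at two-sided 5% with n = 11. The correlation between visits is not in the documents and was varied from 0 to 0.8. For reference, independent tests would give 1 − 0.95³ = 14.3% for three and 1 − 0.95⁴ = 18.5% for four. The tests share a baseline and are correlated, so simulation (12,000 runs per setting) is the better guide:

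| Event | Continuous scores | Whole-number NRS |
|---|---|---|
| Any of three signed-rank tests, either direction | 9.9–11.8% | – |
| Any signed-rank or Friedman, either direction | 11.5–13.3% | 7.0–10.8% (exact p) or 11.2–13.4% (normal approximation) |
| The same, toward less pain only | 5.4–6.4% | 3.5–5.3% (exact p) |

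The continuous results do not depend on the SD. The whole-number results do, because small changes round to zero. The 7.0% end comes from the highest correlation tried, 0.8.

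A single two-sided 5% test allows 2.5% toward less pain. The inflation in that direction is therefore 3.5/2.5 = 1.4 to 6.4/2.5 = 2.6 times. If signed-rank tests were read only after a significant Friedman test, the either-direction rate would be 2.6–3.5%, but the plan states no such gate.

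**4. A non-specific fall shared by both arms.** Assumed: a mean fall of 0.5 or 1.0 points at every visit after baseline, SD of change 2, correlation 0.5, and no difference between arms.

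- Fall of 0.5: the end-of-treatment signed-rank test shows improvement in 9.4% of trials, and at least one of the three does in about 22%.
- Fall of 1.0: 29.0% and about 53 to 54%.

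**5. The remedy under the same conditions.** A Mann-Whitney test on change at end of treatment has a type I error of 4.7–4.9% with no change, and about 4–5% with either shared fall. Taking any of the three visits versus sham without an order gives 12.2–12.7%, so moving to a between-group test does not by itself remove the need for an order.

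**The case against.** The strongest reply is that the plan already contains the hierarchy. The objectives name end of treatment and sham, the sample size rests on Day 1 to Day 10, and the 30- and 60-day scores are for sustainability. The signed-rank sentence is itself labelled as the sustainability analysis. A reader might infer that the plan has no deciding contrast at all, or that any significant visit counts as success. The documents support neither: the contrast and time point are named, and no any-visit rule is written. What stands is that no test in the analysis section corresponds to the named contrast.

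A reader might also infer from the 10 to 13% that the chance of a false benefit claim is 2 to 2.5 times 5%. That figure counts significant worsening as well as improvement. Toward less pain the rate is about 5% in absolute terms, and it is inflated only against the 2.5% that one two-sided test allows. Counting both arms would give larger totals, but a significant change in the sham arm is not a false Scrambler benefit, so those totals do not belong here.

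It can be argued that signed-rank tests after Friedman are follow-up tests by custom, which would bring the rate to about 3%. That is a reasonable reading, but it is unwritten, and a gated within-arm test still says nothing about sham.

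Finally, strict error control for a secondary endpoint in a 22-patient feasibility trial is partly a matter of preference. This lowers the severity. It does not remove the mismatch, given the wording of the objective and the evidence statement.

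**Conclusion.** The point holds as a mismatch between endpoint and test, with an unstated level and order as a secondary matter. As written, the plan can produce a significant pain result in the Scrambler arm that is not a benefit over sham.

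The main size is about 22% or 54% of trials with at least one significant within-arm improvement, if both arms fall by 0.5 or 1.0 points. Those falls, and the correlation of 0.5, are assumptions.

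The multiplicity is smaller: about 3.5 to 6.4% toward less pain against 2.5%, when nothing changes. It rests on an assumed two-sided 5% per test and on unknown correlations.

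Severity is modest: the primary outcome, feasibility and acceptability, is unaffected.

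**What to change.** In the effectiveness paragraph:

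- Name one deciding test at two-sided 5%: Scrambler versus sham on change in NRS from baseline to end of treatment. Mann-Whitney on change would do, and the plan already uses that test for baseline characteristics.
- Test the same contrast at 30 days and then at 60 days in fixed sequence, each only if the one before is significant, or report both as supportive.
- Label the Friedman and within-arm signed-rank results as descriptive. Give estimates with 95% confidence intervals and draw no effectiveness or sustainability claim from their p-values.

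The section is written in the past tense. If results have already been seen, state when the deciding test was specified. The comparator and time point are already in the objectives, so the choice need not be driven by the data.

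The cost is a few sentences, with no new data and no extra patients, and the main contrast keeps its full 5%. The downside is that, under the fixed sequence, a 30- or 60-day benefit cannot be claimed as confirmed if end of treatment is not significant.
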